Participants will have their HAs assessed to ensure proper functioning and adequate amplification prior to testing. The American National Standard Institute S3.22-2009 for electroacoustic assessment will be used to ensure proper HA functioning. Amplification will be evaluated using real-ear measures with the AudioScan Verifit™ (or equivalent) system with speech stimuli for input levels of 50, 60 and 70 dB SPL. The evaluation will be based on the National Acoustic Laboratories' nonlinear fitting procedure, version 2 (NAL-NL2). If the participant's HAs do not meet NAL-NL2 targets within ± 10 dB from 500-4000 Hz, the HAs will be re-programmed until targets are met. If the HAs cannot be adjusted to meet targets, the participant will be fit with clinic loaner HAs. If the severity of the hearing loss or tolerance issues prohibit amplification at the prescribed levels, the HA will be programmed as close as possible to NAL-NL2 targets.

Aided, FM Tone Sound Field Threshold levels

Aided, FM tone threshold levels will be obtained in the sound field for each ear at 250, 500, 1000, 2000, 3000, 4000, and 6000 Hz. When testing the poor ear, the better ear will be plugged and muffed (Howard Leight Pre-Shaped Foam Earplug and Howard Leight Hearing Protection Thunder T1 earmuff) (Howard Leight, 2014a, b). Based on pilot data from Washington University School of Medicine, the plug and muff provided an attenuation average of 48 dB for frequencies 250 – 8000 Hz.

CNC Word Recognition Testing

Two list of the CNC word test will be given to participants at 60 dB SPL in two listening conditions, 1) HA in the better ear only and 2) HA in the poor ear only. When testing the poor ear, the better ear will be plugged and muffed. Testing will determine if the participant meets inclusion criteria.

Alternative Therapy Assessment

Participants who have not previously failed a poor ear HA or BiCROS HA trial will be fit with one of those two HA options. The audiologist will determine which HA to fit based on the participant's hearing loss and preferences. After at least 1 to 2 weeks of use, the

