A record of all adverse events will be kept. No formal statistical hypothesis will be tested. The primary safety endpoint will be 6 months post-implant. Adverse event information through 6 months post-implant will be summarized by event type, severity/seriousness, and whether related to the device and/or implant procedure.

Efficacy

The primary study objective is to obtain preliminary efficacy data in adults with asymmetric hearing loss who receive a CI in the poor hearing ear and maintain a HA in the better hearing ear. Efficacy is defined as post-implant improvement in the poor ear with a CI compared to pre-implant with a HA. Measures are sound field threshold levels and CNC monosyllabic words in quiet.

A secondary objective is to obtain efficacy data related to bimodal hearing. Efficacy is defined as post-implant improvement (CI in poor ear + HA in better ear) compared to the pre-implant best-aided condition (either HAs in both ears, or a HA in the better ear alone for adults with no aidable hearing in the poor ear). Measures are sound localization, speech recognition in noise, speech recognition at soft presentation levels, perceived hearing handicap, and reported quality of life.

Sample Size Justification

The primary efficacy endpoint is change in CNC performance from pre-implant to post-implant, with most of the gain expected to be achieved by 6 months. A clinically meaningful change on the CNC test is .10. In our past research we have found CNC standard deviations that range from .06 to .24. Assuming a correlation between repeated measures of .5 (typical in our work) these values translate into standardized mean differences (Cohen's *d*) ranging from .42 to 1.67. At the minimum effect size, a sample size of 37 is necessary for power of .80, the common standard (Cohen and Cohen, 1983; Keppel, 1991; Cohen, 1992). As indicated, the planned sample size will provide adequate to excellent power to detect clinically meaningful differences. Up to 40 participants will be enrolled to allow for attrition.

Note that the analyses described later will often be more complex than the simple approach used here for power calculations (a dependent means t-test), often involving change over longer periods of time, examining nonlinearity in the change profiles, and including additional predictors (e.g., patient characteristics). The impact of these modifications will generally be to increase power by including additional measures that

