Because of the longitudinal nature of the data, the major analytic approach we will use is hierarchical linear modeling (HLM; Raudenbush and Bryk, 2002; Heck and Thomas, 2009; Hox, 2010; Snijders and Bosker, 2012). We chose this approach because the data have a hierarchical structure, with the measures over time nested within individual patients. Thus for the majority of the analyses, we will use a two-level growth curve model, with both linear growth and quadratic growth (i.e., change in linear growth over time or departure from an overall linear or straight line pattern) included. HLM analysis is particularly well suited for longitudinal data with unequal spacing of measures and occasional missing data, both likely to be true in this study. Standard approaches, such as repeated measures analysis of variance, cannot be used because the measurement spacing will vary at the individual level. Missing data, which is not expected to be substantial, is handled in the HLM approach via maximum likelihood estimation (e.g., Enders, 2010). When HLM is used with smaller samples, standard errors may be reduced, although parameter estimates should not be biased (Raudenbush and Bryk, 2002). Accordingly, it may be necessary to use more conservative significance levels.

Estimation in the HLM approach is best thought of as occurring at different levels. At Level 1 of the statistical model, performance for a particular participant will be estimated as a quadratic polynomial growth curve. This can be described by the following model, using CNC performance as the example outcome:

$$\text{CNC}_{ti} = \pi_{0i} + \pi_{1i} \text{Time}_{ti} + \pi_{2i} \text{Time}_{ti}^2 + \epsilon_{ti}$$

where the CNC performance at time t (e.g., six months) for participant i is estimated to be a function of an intercept (π_{0i}), a linear component for time (π_{1i}), and a quadratic component for time (π_{2i}). The coefficients are expected to vary systematically across patients. At Level 2 of the model, the coefficients from Level 1 are viewed as outcomes that depend on patient characteristics:

$$\begin{aligned}\pi_{0i} &= \beta_{00} + \beta_{01}D_{1i} + \beta_{02}D_{2i} + \beta_{03}D_{3i} + r_{0i} \\ \pi_{1i} &= \beta_{10} + \beta_{11}D_{1i} + \beta_{12}D_{2i} + \beta_{13}D_{3i} + r_{1i} \\ \pi_{2i} &= \beta_{20} + \beta_{21}D_{1i} + \beta_{22}D_{2i} + \beta_{23}D_{3i} + r_{2i}\end{aligned}$$

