The three equations represent the intercept, linear component, and quadratic component of growth, respectively. The variables D_{1i} , D_{2i} , and D_{3i} , represent generic predictors such as dummy codes that could represent the particular center from which a patient's data were collected or patient characteristics (e.g., age) that might moderate the efficacy of the implant. These Level 2 predictors allow for systematic differences in patient performance to be detected.

The HLM approach includes omnibus tests that can be used prior to more focused comparisons so that the Type I error rate is not inflated. Judicious choice of centering the time variable allows targeted inferences about particular follow-up time-points. An important part of the HLM analysis are the diagnostic procedures to check assumptions (e.g., homogeneity of Level 1 variances) or to determine if models can be simplified (e.g., Level 2 residual variances of 0). When necessary, standard model modifications will be applied (e.g., modeling sources of Level 1 heterogeneity).

Some analyses will call for simpler approaches. For example, performance at particular measurement points will be of interest (e.g., at Pre-Implant, at 6 months Post-Implant, or at the conclusion of the study). In these simpler analyses, standard univariate and multivariate procedures (e.g., univariate or multivariate multiple regression [if continuous predictors are included] or analysis of variance [if only discrete predictors are tested]) will be used (Maxwell and Delaney, 1990; Keppel, 1991).

Risk Benefit Statement

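### The main growth model has no term for the switch from hearing aid to implant, so with early gain its single quadratic understates the 3- and 12-month changes and can show a false late decline

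*Combined protocol and SAP*

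**What the plan says.** The Sample Size Justification defines the primary efficacy endpoint as the change in CNC score from pre-implant to post-implant, "with most of the gain expected to be achieved by 6 months". The Efficacy section makes this a comparison of two devices in the same ear: HA before, CI after.

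The Data Analysis section names hierarchical linear modeling as the main approach: "Thus for the majority of the analyses, we will use a two-level growth curve model, with both linear growth and quadratic growth". Its worked example is CNC = intercept + Time + Time² at Level 1. The Level 2 predictors are patient-level (center, age). The section adds: "Judicious choice of centering the time variable allows targeted inferences about particular follow-up time-points". It names "diagnostic procedures to check assumptions (e.g., homogeneity of Level 1 variances") and whether residual variances can be dropped. It also allows an alternative: "Some analyses will call for simpler approaches. For example, performance at particular measurement points will be of interest", with pre-implant, 6 months and study end as examples.

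Time is not defined for the pre-implant score. The poor-ear CNC baseline is taken at the candidacy evaluation (CNC Word Recognition Testing: "Two list of the CNC word test will be given to participants at 60 dB SPL in two listening conditions"). Candidacy Determination places that evaluation within 4 months of surgery, and initial stimulation follows surgery by 2–4 weeks.

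**The concern.** One parabola has to describe two different things: a change of device between the first and second measurements, and learning with the implant afterwards. Level 2 predictors do not vary within a patient, so they cannot code the switch. Centering Time moves the intercept and leaves every fitted value unchanged.

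A parabola cannot rise sharply and then stay flat. If most of the gain is there by 3 months, the least-squares curve starts too high, is too low at 3 months, overshoots in the middle and turns down at the end. The plan says its analyses will often involve change over longer periods and "examining nonlinearity in the change profiles", which are the outputs affected. The results are also meant to shape a Phase III trial, so an artificial late decline or an understated 12-month gain would carry forward.

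**Working it through.** **The plan's own figure.** With "Assuming a correlation between repeated measures of .5 (typical in our work"), the SD of the difference is SD × √(2 × (1 − .5)) = SD. So d = .10/.24 = .42 and .10/.06 = 1.67, as stated. For d = .42, n = 37 gives power .806 in a one-sided paired t-test at .05. (A two-sided test would need 47–48; alpha and sidedness are not stated. That is a separate matter.) The basis for n = 37 is thus a paired difference, not a curve.

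**Fitted changes, baseline coded 0.** With complete data at 0, 3, 6, 9 and 12 months, the fixed effects equal the least-squares quadratic through the visit means y0 to y4. Put

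- L = (−2y0 − y1 + y3 + 2y4)/10
- Q = (2y0 − y1 − 2y2 − y3 + 2y4)/14

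The fitted changes are: pre to 3 months, L − 3Q; pre to 6, 2L − 4Q; pre to 12, 4L; 6 to 12, 2L + 4Q. The profiles below are assumptions, as shares of total gain.

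| True profile (pre/3/6/9/12) | L | Q | Fitted 3 / 6 / 12 | Fitted 6 to 12 |
|---|---|---|---|---|
| Step 0/1/1/1/1 | .200 | −.143 | .63 / .97 / .80 | −.17 |
| Early 0/.8/1/1/1 | .220 | −.129 | .61 / .95 / .88 | −.07 |
| Intermediate 0/.6/.85/.95/1 | .235 | −.089 | .50 / .83 / .94 | +.11 |
| Gradual 0/.5/.8/.95/1 | .245 | −.075 | .47 / .79 / .98 | +.19 |

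No true profile falls.

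**Baseline coded −3 months.** Step: .85/1.03/.91, fall .12. Early: .78/.98/.97, fall .003.

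**Chance of a significant false decline.** Under equal correlation r = .5, the SE of the fitted 6-to-12 change is SD × √(.5 × (.4 + 16/14)/37) = .144 × SD.

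- Early profile, assumed gain 40 points: the fitted fall is .0743 × 40 = 2.97 points. The SE is 3.47 at SD 24 (top of the plan's range) and 2.34 at SD 16.2. A t-test with 36 degrees of freedom is then significant for decline in 13% and 23% of trials (nominal 2.5%). Simulation agrees.
- Same profile and gain at SD 6, the bottom of the range: about 91%.
- Same profile, gain 20: about 6–9%. Gain 10: 4–5%.
- Pure step, gain 40: about 49% at SD 24 and 81% at SD 16.2.
- Early profile, gain 40, baseline at −1 month: 8% and 13%. At −3 months: about 3%.

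**Coverage of the 95% interval for the 12-month change.** The SE is SD × √(.5 × 1.6/37) = .147 × SD. For the early profile with gain 40 the bias is .12 × 40 = 4.8 points, against an SE of 3.53 (SD 24) or 2.38 (SD 16.2). Coverage is 74% and 50%. With gain 20 it is 90% and 84%. For the gradual profile it is about 94% at these SDs.

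**Actual-time coding.** Four months plus 4 weeks puts the earliest baseline about 5 months before stimulation. Assume baselines spread evenly from 0.5 to 5 months before. The fitted curve at stimulation is then already about 27–50% of total gain above its baseline across the step, early and gradual shapes (17–27% for a spread of 0.5 to 2 months). The 6-month change for the early profile runs from 11% low to 2% high, depending on which random terms are kept.

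**The case against.** The documents do not establish the condition that does the harm. They say only that most gain comes by 6 months, with nothing about 3 months. The intermediate profile fits that statement, and there the 12-month change is 6% low, the 6-month change about 2% low, and there is no 6-to-12 fall. Six months is the time-point the plan ties to the primary change, and the error there is 3–5% in the plateau profiles with baseline at 0. At a 40-point gain, the 12-month error (4.8 points early, 8.0 step) is below the plan's meaningful change of 10 points. The plan chose its method because spacing varies by individual, which suggests actual times; an earlier baseline shrinks the false decline for all but a near-pure step. The direct time-point analyses would avoid the problem, and the bias understates gain, so it does not create false efficacy.

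All of this limits the size, and the harms under the two codings are alternatives that must not be added together. It does not remove the gap. The time-point analyses cover only some analyses and are not made the main analysis of the endpoint. The diagnostics are given as examples, but none concerns the fit of the mean curve. Fitting the curve to post-implant visits alone would remove the distortion, but it would no longer estimate the pre-to-post change.

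**Conclusion.** The concern holds on conditional terms. As written, the main model cannot represent the device switch that defines the endpoint, and no stated safeguard corrects this. The size depends on two things the documents leave open: how early the gain comes and how Time is coded. It is material when about 80% or more of the gain is present at 3 months and baseline sits at or near 0. Gain is then understated by 19–37% of the total at 3 months and 12–20% at 12 months, and a plateau can be reported as a decline. It is small for gradual gain with baseline at 0, and for the 6-month change under that coding. The profiles, the 40-point gain and equal correlation over time are assumptions. This should be corrected; it does not invalidate the trial.

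**What to change.** For the pre-to-post change, use one of two models:

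- **Implant indicator** (0 pre, 1 post), with linear and quadratic terms in months since stimulation applying to post-implant visits only. It is exact for the step. It gives .81/.97/.99 at 3/6/12 months for the early profile and .50/.79/1.00 for the gradual one. It keeps actual post-implant timing and adds one mean parameter.
- **Visit as a category** (pre, 3, 6, 9, 12 months) with within-person covariance, reporting the pre-to-6 and pre-to-12 contrasts. It assumes no shape and adds two mean parameters. With complete data the 6-month contrast is the paired difference behind n = 37. It loses some timing information within the ±30-day windows.

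In either case, define Time = 0, state which analysis is the main one for the pre-to-post change, keep the quadratic for the post-implant course, and compare observed visit means with the fitted curve.

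The cost is wording and a line of code; no new data. Under equal correlation and baseline at 0, the variance of each contrast is proportional to its sum of squared weights. For the quadratic this is 1.543 (6 months) and 1.6 (12 months); for categorical visits 2 and 2; for the indicator model 1.55 and 1.95. Standard errors therefore rise by √(2/1.543) = 14% and √(2/1.6) = 12% with categorical visits, and by √(1.55/1.543) = 0% and √(1.95/1.6) = 10% with the indicator.

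### The plan warns that HLM standard errors may be too small in a small sample, but its only remedy is an unnumbered stricter significance level, which leaves standard errors and intervals uncorrected

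*Combined protocol and SAP*

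**What the plan says.** The Data Analysis section makes HLM the main method: "for the majority of the analyses, we will use a two-level growth curve model". The model is quadratic in time and is written out "using CNC performance as the example outcome". The Level 2 equations carry three generic predictors, with "dummy codes that could represent the particular center" given as one possible use.

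Two sentences bear on estimation. The first concerns missing data, which "is handled in the HLM approach via maximum likelihood estimation". The second is a warning: "When HLM is used with smaller samples, standard errors may be reduced, although parameter estimates should not be biased". The response follows at once: "Accordingly, it may be necessary to use more conservative significance levels". No level is given, nor any condition under which it would apply. The section does not mention REML, a degrees-of-freedom correction or the reference distribution for the tests.

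Two other safeguards appear in the section, and neither is offered for this problem. Resampling is reserved for data that no acceptable transformation can make approximately normal. The "omnibus tests that can be used prior to more focused comparisons so that the Type I error rate is not inflated" deal with multiple comparisons, not with the size of a standard error.

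Sample Size Justification gives N = 37 for power .80 at d = .42, based on a dependent-means t-test, with enrolment of up to 40. It states neither alpha nor sidedness, and no other section does.

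**The concern.** Having identified standard errors that are too small, the plan changes the threshold instead of the standard errors. A suitably chosen lower level could restore the size of a given test, but a 95% interval built from the same standard error would still be too narrow. This matters because Study Design says the results will help set the final sample size of a Phase III trial, where the precision of the estimates counts as much as the p-value.

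The remedy also has no reference point. The phrase more conservative means little when no base alpha or sidedness is stated. The same omission affects the power statement, which cannot be interpreted without them.

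**Working it through.** **1. Reproduce the plan's sample size.** Inputs from Sample Size Justification: change of .10; SD .06 to .24; correlation .5; power .80; paired t-test.

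- SD of the change = SD × √(2(1 − .5)) = SD.
- d = .10/.24 = .4167, given as .42; .10/.06 = 1.67. Both match the plan.
- Power comes from the noncentral t distribution with n − 1 df and noncentrality d√n. At n = 37 and d = .42, the noncentrality is .42 × √37 = 2.555.

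| Test level | N for power .80 at d = .42 | Power at n = 37 | Power at n = 40 |
|---|---|---|---|
| One-sided .05 (same as two-sided .10) | 37 | .805 | .833 |
| Two-sided .05 (same as one-sided .025) | 47 | .701 | .736 |
| Two-sided .025 | 57 | .589 | .629 |
| One-sided .01 | 60 | .553 | .594 |
| Two-sided .01 | 70 | .445 | .487 |

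Of the levels tried, only one-sided .05 (equivalently two-sided .10) returns 37. With unrounded d = .4167, power at n = 37 is .800 one-sided and .694 two-sided at .05.

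The two-sided .05 figure depends on the SD. At n = 37 it is .69 to .70 at SD .24 (unrounded or rounded d), .801 at SD .211, .84 at SD .20 and .98 at SD .15. It is therefore at least .80 for SDs up to about .21.

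**2. Size of the standard-error problem.** The plan does not fix the test statistic, so this step rests on assumptions: full maximum likelihood (ML), balanced complete data, and a within-person change contrast whose variance is estimated across n = 37 participants with p Level 2 coefficients (p = 1 with no predictors, p = 4 with three). Three predictors is the number in the plan's equations, and also the number of dummy codes that four centers would need.

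- ML divides the between-participant variance by n; REML divides by n − p. The standard-error ratio is √((n − p)/n).
- p = 1: √(36/37) = .986. p = 4: √(33/37) = .944.
- Actual two-sided error = 2 × P(T > critical value × ratio), with T on n − p df.

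| Reference distribution | p = 1 (36 df) | p = 4 (33 df) |
|---|---|---|
| t, critical value 2.028 / 2.035 | 2 × P(T > 2.000) = 5.3% | 2 × P(T > 1.921) = 6.3% |
| z, critical value 1.960 | 2 × P(T > 1.933) = 6.1% | 2 × P(T > 1.851) = 7.3% |

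Coverage of a nominal 95% interval is 100% minus these figures, so between 94.7% and 92.7%.

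**3. Width of corrected intervals.**

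- Against ML with t: 1/.986 = 1.014 (p = 1) and 1/.944 = 1.059 (p = 4).
- Against ML with z: 2.028/(1.960 × .986) = 1.049 (p = 1) and 2.035/(1.960 × .944) = 1.099 (p = 4).

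The corrected interval is thus about 1% to 10% wider.

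The plan expects "unequal spacing of measures and occasional missing data, both likely to be true in this study". The closed form is therefore an approximation. This is also why a general correction such as Kenward-Roger or Satterthwaite is preferable to a fixed adjustment.

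**The case against.** The strongest reply is that the inflation figures rest on a test the plan never names. Maximum likelihood appears only in the missing-data sentence and is not said to be full rather than restricted; no z or t reference is given. With t and no predictors the excess is 0.3 percentage points. The 7.3% needs a z reference and three predictors, which the plan presents only as generic. This stands: 5.3% to 7.3% is a range over open choices, not an estimate for this trial.

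Second, the Data Analysis section also allows standard univariate and multivariate procedures at particular time points, such as pre-implant and 6 months. Those use ordinary t or F tests and are not affected. The plan does not say whether the main CNC (monosyllabic word test) conclusion will come from these or from HLM. A reader might infer that the primary CNC test runs at 7% error; the documents do not support that.

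Third, a reader might infer that the quoted sentence lets the sponsor relax the threshold once results are known. It permits movement only in the stricter direction. A well-calibrated stricter level would also restore the size of a single test. What it cannot do is correct the intervals, and the plan gives no calibrated level.

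Fourth, a reader might conclude that N = 37 is wrong. It is correct at one-sided .05, and efficacy is worded as improvement, although no one-sided test is named. The .70 applies only at the largest SD in the plan's range.

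Finally, the trial is single-arm and seeks preliminary efficacy data. That limits the weight of the point, but the trial still has a powered primary endpoint and feeds a later trial.

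**Conclusion.** The concern holds in a limited form. The plan names a small-sample defect in its main method and answers it with a conditional, unnumbered threshold that leaves standard errors and intervals uncorrected. A better method is available at almost no cost.

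The size is modest: actual error of about 5.3% to 7.3% against a nominal two-sided 5% at n = 37, assuming full ML, balanced complete data, and between none and three Level 2 predictors. The simpler time-point analyses are outside it.

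The missing alpha and sidedness is a supporting point about missing detail, not evidence of a wrong sample size. It has one practical consequence: at the minimum effect, the stated power of .80 becomes about .70 at n = 37, or .74 if all 40 participants contribute, should the test be two-sided .05.

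**What to change.** In Data Analysis, replace the sentence on stricter levels with: *HLM models are fitted by REML, and tests and confidence intervals for fixed effects use a Kenward-Roger or Satterthwaite small-sample correction, at the same alpha and sidedness as the sample-size statement.*

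In Sample Size Justification, state the level. Either say that N = 37 gives power .80 at d = .42 with one-sided .05 (equivalently two-sided .10), or, if tests are two-sided .05, restate power at the largest SD of .24 as about .70 with 37 participants and .74 with 40, and add that with 37 it is at least .80 for SDs up to about .21.

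The cost is wording and a software option, with no new participants, visits or measurements. Intervals widen by about 1% to 10% relative to uncorrected ML. If two-sided .05 is chosen, the stated power at the minimum effect is less favourable.
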